Anxiety disorders are the most common class of psychopathology among youth, with nearly a quarter of adolescents meeting 12-month diagnostic criteria.¹⁻³ Significant functional impairment is associated with youth anxiety disorders, such as problems with social relationships, performance in school, and physical health conditions.⁴⁻⁶ The negative consequences of anxiety disorders follow youth into their adult lives, including increased risk for psychopathology, such as subsequent depression and substance use problems, and also significant functional impairment in the form of financial problems, poor health, and interpersonal problems.⁷⁻⁹ There is evidence that anxiety prevention services can be effective for youth; however, the majority of effective services are primarily delivered face-to-face, decreasing the potential for scalability.¹⁰⁻¹⁴ The few technology-enabled prevention services tested have not yet translated into significant effects on anxiety outcomes among youth.^{15,16} Given the immersion of digital technology into the lives of this generation of teens, the potential of technology-enabled prevention services for anxiety to reach and engage at-risk youth is extremely promising.¹⁷

Novel approaches to increase engagement in and access to technology-enabled prevention services that prevent the development and impact of anxiety disorders among youth are needed. First, a technology-enabled prevention service needs to be designed that *includes adolescents in the design of the service*. Including adolescents in the design process to create services that meet their needs and fit within their daily lives will result in tools that teens engage with and use.¹⁸ Second, a technology-enabled prevention service needs to be designed that *partners with community organizations*. Community organizations that serve youth provide a unique setting and infrastructure in which to embed technology-enabled prevention services. Utilizing community organizations, especially those programs that primarily serve underserved youth, increase scalability and access to mental health care. Third, technology-enabled prevention service needs to be designed that *explores underlying mechanisms*. While past technology-

enabled prevention services for youth have used evidence-based psychological strategies, they have not used an optimization strategy to evaluate which strategies are the most potent in driving the intervention effects. A widely accessible and available technology-enabled prevention service co-designed by teens and community partners has the potential to reach and engage large populations of youth in need of prevention programs to prevent the deleterious effects of youth anxiety disorders.

The **goals specific to this grant** are to employ user-centered design methods to engage adolescents, providers, and community partners into the iterative design and evaluation of a technology-enabled prevention service for anxiety among youth.

Specific Aim 1: To work with youth and a community organization that serves underserved youth to iteratively design a technology-enabled prevention service for anxiety.

The co-design process will involve user-centered design workshops with youth at risk for anxiety psychopathology from the community-based [REDACTED] teen program and their staff. Based on the feedback elicited from the design workshops, the PI will work with a software development team to adapt the technology-enabled prevention service. The PI will then conduct usability testing in the laboratory and in the field on the adapted prototype to iteratively refine features (with the software development team) to ensure that the prototype is usable and useful for at-risk adolescents in community settings.

Specific Aim 2: To conduct an 8-week randomized pilot trial evaluating the adapted technology-enabled prevention service for anxiety among 80 youth with elevated anxiety from a community organization that serves underserved youth. We will use a 2³ factorial experimental design for the pilot trial. The goals of the trial are to a) evaluate the feasibility and acceptability of the technology-enabled prevention service for anxiety designed in Aim 1 with adolescents in a community setting (**Aim 2a**), b) estimate the effects of the intervention components on anxiety symptoms, as well as on the psychological (i.e., avoidance, cognitive biases, and emotion dysregulation) and engagement targets (**Aim 2b**), and c) estimate if the targeted psychological and engagement targets mediate the relation between the intervention components and anxiety symptoms (**Aim 2c**).

Specific Aim 3. To form and convene two advisory boards comprised of local and national members, as well as to partner with a Teen Investigator on these activities. We recently received seed grant funding through Northwestern's Alliance for Research with Chicagoland Communities (ARCC) to form and convene diverse advisory boards, one teen-based and one adult-based, with varying perspectives to oversee and provide feedback on the delivery, implementation, community impact, and scale-up of a technology-enabled prevention service for youth anxiety. The goals of these boards are for members to provide input on what can be done to advance the delivery and implementation of the technology-enabled prevention service for teen anxiety, as well as provide high-level guidance on community impact and on subsequent scale-up efforts in other settings that serve underserved youth. We will also recruit 1 Teen Investigator from the [REDACTED] teen program to work with us in preparing and leading the advisory board meetings, as well as helping with data analysis and dissemination of data from the board meetings. Upon consultation with the IRB reviewer, there is agreement that the activities related to Aim 3 (i.e., the teen and adult advisory boards, as well as the role of the Teen Investigator) are not considered human subjects research, nor is there research intent for these activities; thus, there is no NU IRB requirements for this type of material.

2.0 Enrollment Criteria (who can be in your study and who would not be eligible to participate in your study):

Study 1a. We will recruit 10 adolescents aged 12-18 years from the [REDACTED] led by the teen services staff within the [REDACTED] to participate in two 75min **design workshops**. Adolescent participants will have total Spence Children's Anxiety Scale- Short Version (SCAS) scores > 1 SD above the mean (i.e., ≥ 23).⁴⁷ We chose this cutoff point because individuals with SCAS scores in this range are at increased risk of anxiety

problems.⁴⁷ In addition, exclusionary criteria for youth include: (a) current or past diagnosis of anxiety disorder; (b) current psychotic disorder; (c) not owning a smartphone with internet service; and (d) inability to provide assent and obtain verbal guardian consent.

Study 1b. We will recruit 10 adult (18 \geq years) staff members working with [REDACTED] teen services to participate in two 75min **design workshops**. No exclusionary criteria will be included, in that we will invite each staff member to participate in the design workshops. Participation will be completely voluntary.

Study 2a. We will recruit 10 adolescents aged 12-18 years from the [REDACTED] program to participate in one 60-minute **laboratory usability session**. Adolescent participants will have total Spence Children's Anxiety Scale- Short Version (SCAS) scores > 1 SD above the mean (i.e., ≥ 23).⁴⁷ In addition, exclusionary criteria for youth include: (a) current or past diagnosis of anxiety disorder; (b) current psychotic disorder; (c) not owning a smartphone with internet service; and (d) inability to provide assent and obtain verbal guardian consent.

Study 2b. We will recruit 10 adult (18 \geq years) staff members working with [REDACTED] teen services to participate in one 60-minute **laboratory usability session**. No exclusionary criteria will be included, in that we will invite each staff member to participate in the laboratory usability session. Participation will be completely voluntary.

Of note, the current protocol will be revised in a subsequent modification to reflect additional project information, including participant-facing materials, for the later phases (i.e., the 8-week **usability field trial** [Study 3]) and the 8-week **randomized pilot trial** [Study 4]).

3.0 Sample Size:

Ten participants typically identify 95% of usability issues. For 80 participants, we will be able to detect an effect of $d = .65$ based on two groups with 80% power at a type I error rate of .05 using an independent t-test. Accordingly, the maximum numbers of participants to be included in studies are:

Study 1a: 10 adolescents aged 12-18 years

Study 1b: 10 (adult 18 \geq years) [REDACTED] teen services staff

Study 2a: 10 adolescents aged 12-18 years

Study 2b: 10 (adult 18 \geq years) [REDACTED] teen services staff

4.0 Recruitment and Screening Methods:

Study Recruitment. We will work with [REDACTED] staff to recruit youth for the research study. This will involve distributing flyers throughout the [REDACTED] and also the [REDACTED] communication staff posting about the study via [REDACTED] digital media outlets (e.g., twitter, website, etc.; see advertisement text document). [REDACTED] staff will also recruit adolescents via word of mouth, indicating the research opportunity involves helping Northwestern researchers and developers create a digital program to assist youth to deal more effectively with anxiety and stress. They will also indicate that they would be paid for their time and need their parent or guardian's verbal consent to participate. Importantly, [REDACTED] staff will broadly disseminate information about the study to all adolescent members aged 12-18 years. [REDACTED] staff will not single out, or approach, adolescents they believe to be experiencing mental or emotional health issues. Interested adolescents will be given a flyer with more information and directed to include their parent/guardian in contacting the research team and/or accessing the hyperlink for the brief screening survey. If eligible for the study, the adolescent will be asked to provide their email along with their parent/guardians' email, and we will send an email to introduce the study and setup a phone call with the parent/guardian and adolescent.

Adolescent Eligibility Screening Process for Study 1a and 2a. Identical to approved screening survey methods used in [REDACTED], interested adolescents will be directed to take a brief online screening survey or contact the research team with the permission of their parent or guardian.³⁷ The first page of the survey will contain an online parental consent form describing the contents, purpose, and duration of this brief, anonymous screener. Text will indicate that the purpose of the study is to recruit adolescents for a workshop/usability session of which the goal is to help with the design and testing of a smartphone application (app) designed to assist youth to understand and deal more effectively with emotions, like stress and anxiety. If parental permission is provided, the second page will contain an online adolescent assent form with identical information as the parental permission form. The following survey will include three areas of criteria to determine eligibility (i.e., aged 12-18 years, correctly answering the data quality-check question, and scoring 22 or below on the SCAS). Ineligible participants will be directed out of the survey and thanked for their time. Online parental permission and online adolescent assent will be attained, but to protect the anonymity of the adolescents, we will not collect written documentation of adolescent assent or parental consent for this brief screening survey. Importantly, there is no more than minimal risk involved in completion of the brief online survey and adolescents' answers will remain completely anonymous (no IP addresses will be automatically logged in REDCap).

Those eligible will be asked if they remain interested in the research opportunity that involves helping Northwestern developers create a smartphone app to assist youth to deal more effectively with stress and anxiety. This request will indicate that they would be paid for their time and need their parent's consent to participate. Those interested will be asked to click a hyperlink within the survey that will redirect them to separate survey hosted on REDCap and the adolescent will be asked to provide her/his email along with their parent's email. There will be no link between the answers to the brief screening survey and the survey asking for parent and adolescent email.

We will contact the parent and adolescent via email to tell them more information about the study. If the parent and adolescent indicate interest in hearing more about the study upon contact, we will then setup a phone call with both the parent and adolescent to go over the study procedures and the consent and assent forms and answer any questions or concerns they may have prior to agreeing to participate in the study. In this process, the parent/guardian and adolescent will be fully informed of all activities related to the investigation, the types of assessments and procedures, the right to discontinue participation at any time for any reason, and the potential risks associated with study procedures addressed in the parental permission/assent forms. Once the forms are reviewed, all questions/concerns are addressed, and the adolescent confirms interest in participating in the study, we will document the verbal informed consent/assent and documentation will be securely stored in a locked cabinet at the Center for Behavioral Intervention Technologies (CBITs). If the parent and adolescent are not available at the same time, we will first talk to the parent to attain verbal parental permission over the phone, and then get in contact with the adolescent to attain verbal assent after parental permission is received. Eligible and consented adolescents will be scheduled for the workshop at the [REDACTED].

5.0 Research Locations:

The adolescent and staff design workshops (Study 1a & Study1b) and laboratory usability session (Study 2a & Study 2b) will be conducted at the [REDACTED]. [REDACTED] has developed a youth development program called [REDACTED]. This program is specifically designed for teens, and by teens, that focuses on the social-emotional and academic development of youth. The [REDACTED] is a social service system for seven communities west of Chicago, which includes socioeconomically diverse neighborhoods with variant access to mental health resources. The [REDACTED] anchors social service and public safety services under the directorship of [REDACTED] and strategically targets community partners and youth development programming. Director [REDACTED] leads the [REDACTED].

program, supporting the associated teen services staff. As a recent extension of social service, the [REDACTED] just started deploying mental health services to children, youth, and adult patrons of their [REDACTED]. All in-person sessions for Studies 1-4 will take place in a private room within the [REDACTED] to ensure participant confidentiality and privacy. Required permissions and approvals will be obtained at that location prior to project deployment.

6.0 Multi-site Research (research that involves external collaborating institutions and individuals):

N/A

7.0 International Research (where data collection will occur outside the United States and U.S. territories, including online activities)

N/A

8.0 Procedures Involved:

Note: We are currently planning for the described study procedures to occur in person as proposed (5-year timeline beginning July 1; see Table 3 Timeline); however, in the event this is not possible given the current pandemic, all in-person procedures in Studies 1-4 will be conducted remotely over Zoom. Precautions will be taken to protect the meeting from being accessed by others, such as password-protecting the meeting and not allowing entry into the meeting until the host arrives. We will record the Zoom sessions and store those recordings on the secure server hosted by Northwestern University. Participants will be compensated in electronic Visa gift cards for their efforts.

Study 1a. Ten adolescents will be asked to complete two individual *design workshops* lasting around 75min. The first design workshop will involve the method of ‘zine-making.’ In zine-making, we will ask adolescents to draw, write, and/or collage several ‘snapshots’ of their experiences regarding feeling stressed/anxious and managing that anxiety, resulting in the creation of a small story of adolescents’ most recent experiences with stress and anxiety. The second design workshop will use the HCI ‘think aloud’ method. In this exercise, we will provide adolescents a phone with the original adult IntelliCare apps installed on it (or ask them to download the apps on their own smartphone if remote). We will ask them to verbalize their thoughts while they navigate through the IntelliCare program to complete a set of tasks. The data collected will be to help inform the design of the digital tool for anxiety prevention, and how it can be integrated into the current lives of adolescents. At the end of each of the 75min sessions, adolescents will be thanked, comprehensively debriefed, and given \$25 for their participation (\$50 total if both sessions are completed).

Study 1b. We will recruit 10 adult (18 ≥ years) staff members working with [REDACTED]’s teen services to participate in two, 75m design workshops. We will invite all staff members to participate in the research opportunity and underscore that their participation is completely voluntary. Interested staff will be scheduled individual sessions at the [REDACTED]. Staff will be asked to complete a two-session, individual *design workshops*. The first design workshop will utilize the HCI method of zine-making. We will ask the staff to draw, write, and/or collage several ‘snapshots’ of their current workflow at the [REDACTED], and how a digital intervention for youth anxiety could be incorporated into this workflow at the [REDACTED]. The second design workshop will use the HCI ‘think aloud’ method. In this exercise, we will provide staff a phone with the original IntelliCare coaching dashboard installed on it (or ask them to download the dashboard on their own smartphone if remote). We will ask them to verbalize their thoughts while they navigate through the coaching dashboard to complete a set of tasks. The data collected will be to help inform the design of the coaching platform associated with the digital tool for adolescent anxiety prevention, and how it can be integrated into the current workflows of [REDACTED] teen services staff. At the end of each of the 75min sessions, staff will be thanked, comprehensively debriefed, and given \$25 for their participation (\$50 total if

both sessions are completed).

Study 2. Laboratory usability testing will evaluate the usability of the apps and coaching dashboard prototypes. As 10 participants typically identify 95% of usability issues, we will recruit 10 new adolescents aged 12-18 years and 10 teen services staff to participate in 60-minute laboratory sessions.⁵² Adolescents will be enrolled in waves of 3-4, and staff will also be enrolled in waves of 3-4. The “think aloud” method will be used, in which adolescents and staff will be asked to verbalize their thoughts when using the functioning prototypes of the IntelliCare apps (for adolescents) or coaching dashboard (for staff) to complete specific tasks (e.g., attain a badge in Thought Challenger; check adolescents’ progress on dashboard). This process will be used to identify problems early in the design process, such as features leading to user confusion, error, or dislike.^{53,54} The PI will work iteratively with the waves of adolescents and staff to address the problems identified by prior groups before the next group tests the refined prototypes. Adolescents and staff will be administered the System Usability Scale (SUS)⁵⁵ to obtain quantifiable measures of usability. Sessions will be recorded and observation notes will be taken. Screen capture software will be used to record progression through the tasks. At the end of the 60min session, they will be thanked, comprehensively debriefed, and given \$25 for their participation. See Table 3 for our working timeline.

Table 3. Timeline

Study	Activity	Year 1		Year 2		Year 3		Year 4		Year 5	
		1-6	7-12	13-18	19-24	25-30	31-36	37-42	43-48	49-54	55-60
Studies 1-3: Design Workshops & Usability Testing	Adapt IntelliCare to Youth Digital Prototype	X									
	Design Workshops and Refinements	X	X								
	Usability Laboratory Testing and Refinements		X	X							
	Usability Field Trial and Refinements			X	X						
	Finalize Digital Prototype for Pilot Trial				X						
Study 4: Pilot Trial	Recruit and Enroll Adolescent Participants					X	X	X	X		
	Deliver the Intervention					X	X	X	X		
	Conduct 6-mon Follow-up Assessments						X	X	X	X	
	Analyze Trial Data									X	X
	Write and Submit NIH R01 Grant							X	X	X	X
	Submit Manuscripts and Conference Abstracts	X	X	X	X	X	X	X	X	X	X

9.0 Research with Vulnerable Populations (if children are the ONLY vulnerable population you plan to enroll, do NOT complete this section -- instead fill out Appendix A)

Children are the only vulnerable population; see Appendix A.

10.0 Incomplete Disclosure or Deception:

N/A

11.0 Consent Process:

Brief Online Screening Survey (Study 1a, Study 2a)

Identical to approved screening survey methods used in [REDACTED], the first and second page of the survey will contain an online parental permission form and an online adolescent assent form describing the contents, purpose, and duration of this brief, anonymous screener. The online adolescent assent form will be available only if parental consent is given. Text will indicate that the purpose of the study is to recruit adolescents for a workshop (for Study 1a)/usability session at the [REDACTED] (Study 2a), of which the broader goal is to help with the design and testing of a smartphone application (app) designed to assist youth to understand and deal more effectively with stress and anxiety. Text will also indicate that survey answers are anonymous and will be kept completely private. The text encourages adolescents to talk about the survey with their parents or a trusted adult, and for both the adolescent and parent to visit the webpages provided giving information about our center and institution. Lastly, the text indicates

participation is completely voluntary and that the adolescent will be asked to provide their email, along with their guardian/parent's email if eligible for the relevant study. If the parent does not agree for their child to participate in the study or if the adolescent does not agree to participate, the adolescent will be directed to the end of the survey. Further, if the adolescent indicates they are out of the age range of 12-18 years, do not answer the automation preventative question confirming they are a real person, or score 22 or below on the SCAS, they will also be directed to the end of the survey. Online parental permission and online adolescent assent will be attained. To protect the anonymity of the adolescents, we will not collect written documentation of adolescent assent or parental consent for this brief screening survey. Importantly, there is no more than minimal risk involved in completion of the brief online survey and adolescents' answers will remain completely anonymous (no IP addresses will be automatically logged in REDCap).

Consent and Assent Process for Adolescent Studies (Study 1a, Study 2a)

If the parent and adolescent indicate interest in hearing more about the study upon email contact, we will setup a phone call with both the parent/legal guardian and adolescent to go over the study procedures and the consent and assent forms and answer any questions or concerns they may have prior to agreeing to participate in the study. We will send the parental permission and adolescent assent forms via email prior to the scheduled phone call for parent-adolescent dyad to review. The adolescent and parent will also have the opportunity to read through the forms at the beginning of the phone call if they have not done so already. During the scheduled phone call with both the adolescent and parent, they will be fully informed of all activities related to the investigation, the types of assessments and procedures, the right to discontinue participation at any time for any reason, and the potential risks associated with study procedures addressed in the parental permission/assent forms. During this discussion, we will emphasize it is very important to us that they understand the procedures, risks and benefits, and other consent components prior to providing their consent/assent. We will also encourage the parents and adolescents to ask questions on anything that is not clear. After which, we will ask the parental/guardian if they are willing for their child to participate in the relevant study and document their verbal parental permission. Next, we will ask the adolescent if they are interested in participating in the relevant study and document their verbal assent. If the parent and adolescent are not available at the same time, we will first talk to the parent to attain verbal parental permission over the phone, and then get in contact with the adolescent to attain verbal assent after parental permission is received. Once the permission and assent forms are reviewed, all questions/concerns are addressed, and the parent/guardian and adolescent confirm permission/interest to participate in the study, we will schedule the study session at the [REDACTED]. If adolescents aged 18 years provide their permission to participate, they will be asked to provide their signature on the consent form. The verbal parental permission forms and adolescent assent forms and documentation will be securely stored in a locked cabinet at the Center for Behavioral Intervention Technologies (CBITs). Finally, in compliance with HRP-090 and 091, participants will be provided the opportunity to receive copies of the signed and dated consent and assent forms.

Consent Process for the Staff Studies (Study 1b, Study 2b)

Staff affiliated with the [REDACTED] will be provided with a paper consent form at the beginning of the one-on-one session. The researchers will allow time for staff to read the form and will offer to address any questions or concerns that the staff may have before they sign the consent document. Participants will be informed of the optional nature of this study, that all questions are optional, and that the session will be audio and video-recorded. Participants will be informed that participation in this study is not a job requirement, and given the opportunity to ask any questions. The amount of time devoted to this process will be approximately 5-10 minutes at the beginning of the session. If participants are willing to take part, they will be asked to sign and date the consent form.

On the consent form, participants will have the option to provide optional consent to be contacted for future projects. However, any future projects would involve their own consent processes, and their consent to be contacted will not affect their participation in the current project. Finally, in compliance with HRP-090 and 091, participants will be provided the opportunity to receive copies of the signed and dated consent form.

12.0 Waiver of Participant Signature on Consent Form:

Online parental permission and online adolescent assent will be attained for the brief online screening survey, but to protect the anonymity of the adolescents, we will not collect written documentation of adolescent assent or parental consent.

Verbal parental permission will be attained for adolescent studies, but to decrease barriers to adolescent participation, we will not collect written documentation of parental consent. Verbal adolescent consent will also be attained for adolescents aged 17 years or younger at the same time as verbal parental permission is being attained, or after if the teen is unavailable during phone call with the parent.

13.0 Waivers and Alterations of Consent Information:

N/A

14.0 Financial Compensation:

Study 1a. Adolescents will be given \$25 cash per design session (\$50 total).

Study 1b. Adult staff will be compensated \$25 cash per design session (\$50 total).

Study 2a. Adolescents will be given \$25 cash for the laboratory usability session.

Study 2b. Adult staff will be compensated \$25 cash for the laboratory usability session.

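### Section 4.0 makes a SCAS score of 22 or below a condition for entry, the exact reverse of the 23-or-above rule in Sections 2.0 and 11.0

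*Protocol*

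**What the plan says.** Section 4.0 (Adolescent Eligibility Screening Process for Study 1a and 2a) introduces the screener with "The following survey will include three areas of criteria to determine eligibility". It then names three: being aged 12 to 18, "correctly answering the data quality-check question, and scoring 22 or below on the SCAS". The sentence after the list gives the consequence: "Ineligible participants will be directed out of the survey and thanked for their time".

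Section 2.0 (Enrollment Criteria) gives the SCAS rule for Study 1a and repeats it for Study 2a: "scores > 1 SD above the mean (i.e., ≥ 23". Under Study 1a it adds the reason: "We chose this cutoff point because individuals with SCAS scores in this range are at increased risk of anxiety" problems.

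Section 11.0 (Consent Process, Brief Online Screening Survey) describes the same screener. Adolescents outside the age range, those who do not answer the check question, "or score 22 or below on the SCAS, they will also be directed to the end of the survey".

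Specific Aim 1 describes the intended participants: "user-centered design workshops with youth at risk for anxiety psychopathology".

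**The concern.** Section 4.0 is where a reader looks for the working rule of the screener, and read literally it admits the group that Section 2.0 excludes. Anyone setting up the survey branching from that paragraph would release every adolescent at or above the cutoff and keep those below it. The design workshops and laboratory usability sessions would then reflect the experience of youth who are not in the at-risk group, and those sessions shape the prototype carried into the field trial and the pilot trial.

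The error would also be hard to notice. The screener is anonymous, and Section 4.0 states: "There will be no link between the answers to the brief screening survey and the survey asking for parent and adolescent email". The consent call (Sections 4.0 and 11.0) and the session procedures (Section 8.0) describe no second SCAS. The only scale named for the Study 2 sessions is the System Usability Scale. An adolescent wrongly admitted could not be identified afterwards from the contact records.

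**Working it through.** The check is a comparison of cutoffs. It assumes whole-number SCAS totals, as the protocol's own pairing of 22 or below with 23 or above implies.

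**The rules side by side**

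| Place | How the SCAS item is framed | Scores that proceed |
|---|---|---|
| Section 2.0, Study 1a | requirement for entry | 23 or above |
| Section 2.0, Study 2a | requirement for entry | 23 or above |
| Section 11.0, screener | reason to leave the survey at 22 or below | 23 or above |
| Section 4.0, screener | criterion that determines eligibility | 22 or below |

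**Overlap.** Let A = {score ≥ 23} (Section 2.0), B = {score ≤ 22} (Section 4.0) and C = {score not ≤ 22} (Section 11.0).

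- A ∩ B is empty: no score satisfies both Section 2.0 and Section 4.0.
- A ∪ B is every score: the two rules are exact complements.
- C = A: Section 11.0 and Section 2.0 admit the same adolescents.

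An enumeration over whole-number scores confirmed all three results.

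**Could Section 4.0 be read as a list of exclusions?** No. Its other two items, being within the age range and answering the check correctly, are things a respondent must satisfy. An exclusion reading of the SCAS item alone would break the list. In Section 11.0 every item is worded as a failure (outside the age range, check not answered, 22 or below), so the SCAS phrase fits there. The likely explanation is that the exclusion wording was placed in a list of inclusions without being turned round.

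**Rough size in a reference population.** The protocol equates 23 or above with more than 1 SD above the mean but gives no distribution, so the following is illustrative.

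- If scores were normal: P(Z > 1) = 0.159, so Section 2.0 would select about 16% and Section 4.0 would pass 1 − 0.159 = 0.841, about 84%.
- For any distribution, the one-sided Chebyshev (Cantelli) bound gives P(more than 1 SD above the mean) ≤ 1/(1 + 1²) = 0.5, so Section 4.0 would pass at least 50%.

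These shares refer to the population behind the mean and SD, not to volunteers answering an advertisement about stress and anxiety. The contradiction does not depend on them.

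**The case against.** The strongest reply is that the correct rule is already in the protocol, with its reason, and in more places than the wrong one. Section 2.0 states it twice, Section 11.0 spells out the survey exits correctly, and Aim 1 names at-risk youth. Harm would require someone to follow Section 4.0 and disregard the rest. Section 4.0 also says that the method copies an approved screener from another project, so the branching may never have been built from this sentence. The built survey is not shown. Adolescents may also contact the research team instead of using the survey, and it is not stated whether that route applies the same logic. Finally, Studies 1a and 2a are small qualitative and usability studies, so no randomised comparison or error rate is affected.

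Most of this stands, and it limits what can be claimed. Operational harm is possible but not shown. A score of 22 or below means below the elevated-anxiety cutoff, not low anxiety, since it includes average and moderately raised scores. Whether the Study 4 pilot would use the same screener is unknown, because Section 2.0 defers that material to a later modification. None of this removes the contradiction: two sections describe one survey and give it opposite exits.

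**Conclusion.** The concern holds. Section 4.0 reverses the SCAS criterion set in Section 2.0 and applied in Section 11.0, and the reversal is complete: the two eligible sets have no score in common. It directly affects Studies 1a and 2a, with a maximum of 10 adolescents each (10 + 10 = 20). Followed as written, all of those screened by the survey would lie outside the target group.

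The conclusion rests only on the wording and on whole-number scores. The 84% figure needs normality and is an illustration. The intended direction is not in doubt, so this is best regarded as a drafting error. It must nevertheless be fixed, because it inverts the main inclusion criterion in the section that describes screening, and no later step described in the protocol would catch the mistake.

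**What to change.** In Section 4.0, change the SCAS item in the eligibility list to a score of 23 or above, so that it agrees with Section 2.0 (Studies 1a and 2a) and Section 11.0. Before release, run test entries through the REDCap survey at scores of 22 and 23 and confirm that 22 exits and 23 proceeds. If the screener is already in use, confirm which direction its branching took. When the Study 3 and Study 4 material is added, carry the corrected wording forward if the same screener is used.

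The cost is one phrase in the next protocol modification and a brief check of the survey logic. Sample size, procedures and timeline do not change.
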